8.1.10. Other Safety Data

None.

8.1.11. Concomitant Treatments

All concomitant medication(s) as well as non-drug treatment(s) will be summarized and listed. Summaries will be done by study part and and cohort, as well as across the entire study.

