5.9. Prohibited Treatments and Medications during the Study

5.9.1. Part 2

- Systemic corticosteroids.
- Topical oxymetazoline (outside of study procedures: nasal endoscopy).
- Monoclonal antibody (mAB) or immunosuppressive treatment.
- Anti-immunoglobulin E (IgE) therapy (omalizumab).
- Anti-IL-5 (eg, mepolizumab) therapy.
- Leukotriene antagonists/modifiers unless patient is on a continuous treatment for at least 28 days prior to Screening.

Patients with CRSwNP and asthma randomized into the study will be on standard of care treatment for their disease at time of randomization as prescribed by their physician that will not include prohibited concomitant medications as noted in Section 5.9.1. Subjects that are randomized into the study will continue on their baseline treatment regimen during the study. Subjects randomized into the study will additionally have access to standard of care therapy, that may include the prohibited treatments and medications defined in Section 5.9.1, if such additional therapy is deemed necessary to treat their underlying disease. A protocol deviation is to be completed for any patient that takes a prohibited treatment or medication during the study and the Sponsor is to be notified. The patient may be replaced at the discretion of the principal investigator and/or the Sponsor.

5.9.2. Part 3

Subjects are required to discontinue and avoid using certain medications and treatments (per inclusion and exclusion criteria in Section 4.1.1.1 and 4.1.2.1). Subjects should be instructed at each visit to contact the study site investigator promptly if there are any intended changes or additions to concomitant medications. These include:

- Systemic and parenteral corticosteroids.
- Leukotriene antagonists/modifiers unless patient is on a stable dose.
- Anti-IL-33 targeted therapies.
- Anti-IL-4 and/or IL-13 targeted therapies (eg, dupilumab, lebrkizumab, tralokinumab).
- Mepolizumab, reslizumab.
- Benralizumab.

- Any cell-depleting agents including but not limited to rituximab.
- Any JAK inhibitors.
- Other biologics.
- Investigational drugs.
- Live or attenuated vaccines.
- Oral immune suppressants (eg, cyclosporine A [CsA], azathioprine, MTX, Celcept, mycophenolate-mofetil, IFN-γ).
- Oral or topical phosphodiesterase (PDE) 3 or PDE4 anatgonists (eg, apremilast, crisaborole).
- Oral/topical histamine H4 antagonists.
- Phototherapy (NB-UVB) or broad band phototherapy.

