5.9.2.1. Rescue Medications

Subjects randomized into the study are allowed to take other treatments for their disease as prescribed by the investigator provided they are not included among the prohibited concomitant medications (noted in Section 5.9.2) and the concomitant drugs and doses are maintained unchanged throughout the first 16 weeks of the study. Although no specific rescue treatment is recommended, subjects randomized into the study may have access to standard of care therapy, that may include prohibited treatments and medications defined in Section 5.9.2, if deemed necessary by the investigator to treat their underlying disease.

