Figure 1 demonstrates the study design with the select SAD cohorts rolling over into the multiple dose component. Depending on the safety, ^{CCI} and pharmacokinetic data available, dose escalation may be adjusted to doses other than those planned in the study. Intermediate doses can be evaluated instead of or in addition to the planned dose levels. A possible dosing scenario is included in the schematic.

• Cohort 1 (n=8): 10 mg active (n=6) or placebo (n=2), IV.

- Cohort 2 (n=8): 30 mg active (n=6) or placebo (n=2), IV.
- Cohort 3 (n=8): 100 mg active (n=6) or placebo (n=2), IV x 2 doses. [n=4 in MAD cohort].
- Cohort 4 (n=8): 300 mg active (n=6) or placebo (n=2), IV x 2 doses. [no MAD].
- Cohort 5 (n=8): 1000 mg active (n=6) or placebo (n=2), IV x 2 doses. [no MAD].
- *Cohort 6 (n=8): 2000 mg active (n=6) or placebo (n=2), IV.* [dose escalation stopped before 2000 mg dose group].
- Cohort 7 (n=8): 100 mg (first dose) followed by 300 mg (second dose) active (n=6) or placebo (n=2), SC. [Second dose not given, 100 mg dose changed to 30 mg].

2.2. Part 2:

One or more cohorts of CRSwNP patients will receive a single dose of PF-06817024. Randomization will occur after safety data from Day 8 and PK data through at least Day 5 of the same or higher dose in Part 1 of the study has been reviewed and deemed safe.

• Cohorts 8 and 9: Subjects in each cohort will be randomized in either a 1:1 or 2:1 (PF-06817024: placebo) ratio, depending on the number of cohorts and the emerging data. Up to approximately 10 active (per dose) and approximately 15 placebo (overall) subjects will be enrolled in Part 2 for a planned total of up to approximately 35 subjects.

2.3. Part 3

- Part 3 will consist of a single cohort of subjects with moderate to severe AD
- Cohort 13: Approximately 20 subjects in this cohort will be randomized to receive PF-06817024 or placebo in a 3:1 ratio (PF-06817024: placebo). Additional subjects up to a total of approximately 32 [28 actually enrolled] may be enrolled in a 3: 1 ratio (PF-06817024: placebo) CCI Subjects in this cohort randomized to PF-06817024 will receive a planned dosing regimen consisting of a 600 mg IV loading dose followed by 3 doses of 300 mg IV every 4 weeks.

Note that subjects were randomized 2:1 by site under protocol amendment 4 and then randomized centrally in a 3:1 ratio under amendment 5.

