8.1.5. Discontinuation(s)

Subject discontinuations, temporary discontinuations or dose reductions due to adverse events will be detailed and summarized by treatment. Data will be presented by study part (SAD/MAD, Nasal Polyps and Atopic Dermatitis) and cumulatively across all study parts.

Data will be reported in accordance with the sponsor reporting standards.

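### SAP 8.1.11 summarises concomitant treatment by part and cohort but not by arm, so no planned summary shows whether permitted rescue or prohibited therapy differed between PF-06817024 and placebo in Parts 2 and 3

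*SAP*

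**What the plan says.** SAP 8.1.11 has two relevant sentences. The first plans the outputs: "All concomitant medication(s) as well as non-drug treatment(s) will be summarized and listed". The second fixes the grouping: "Summaries will be done by study part and and cohort, as well as across the entire study".

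On therapy during the study, protocol 5.9.1 says of Part 2: "Subjects randomized into the study will additionally have access to standard of care therapy, that may include the prohibited treatments and medications". Protocol 5.9.2.1 says of Part 3 that "subjects randomized into the study may have access to standard of care therapy, that may include prohibited treatments and medications defined in Section 5.9.2", where the investigator judges it necessary. In both parts, taking a prohibited treatment is recorded as a protocol deviation and the sponsor is told. Protocol 5.8.2 and 5.8.3 require each concomitant treatment to be recorded with its indication, daily dose, and start and stop dates.

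On structure, SAP 2.3 states: "Part 3 will consist of a single cohort of subjects with moderate to severe AD". It adds that 28 subjects were enrolled, randomised 2:1 under protocol amendment 4 and 3:1 under amendment 5. It does not give the resulting arm sizes.

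**The concern.** The primary endpoints (protocol 2.2.1) are adverse events, laboratory findings, vital signs and ECG. SAP 8.1.7 to 8.1.9 present the last three by treatment, and 8.1.8 adds dose-minus-placebo differences in blood pressure and pulse rate with 90% confidence intervals. Someone reading those results needs to know whether the arms took different background or rescue therapy.

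The protocol itself links such therapy to safety. Section 5.8.3 asks that new or changed concomitant medication be evaluated for new or worsening adverse events. Section 8.3 counts worsening of the underlying disease as an adverse event, and that worsening is what rescue would treat. If use differed by arm, part of an apparent safety difference, or of an apparent lack of one, could reflect the added therapy. A table that pools the arms gives no warning of this.

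**Working it through.** There is no plan figure to reproduce. The check is a comparison of text, followed by a small illustration.

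**Step 1: does a cohort contain both arms?** Yes, in every part.
- Part 1: 6:2 active to placebo in each cohort (protocol 4.2).
- Part 2: 1:1 or 2:1 within each cohort (protocol 4.2, SAP 2.2).
- Part 3: one cohort, 2:1 and then 3:1 (SAP 2.3). Here part and cohort are the same group, so naming both adds nothing.

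**Step 2: what grouping do neighbouring SAP sections state?**
- 8.1.5, discontinuations: "dose reductions due to adverse events will be detailed and summarized by treatment".
- 8.1.7, laboratory data: by treatment.
- 8.1.8 and 8.1.9, vital signs and ECG: by cohort and treatment.
- 8.1.4, demographics: by sex within cohort; treatment not named; sponsor reporting standards invoked.
- 8.1.6, adverse events: by part and cumulatively; treatment not named; sponsor reporting standards invoked.
- 8.1.11, concomitant treatment: by part, cohort and whole study; treatment not named; no reference to sponsor reporting standards.

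So 8.1.11 states its own grouping, leaves treatment out, and does not point to a standard that might supply it.

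**Step 3: what else would show use by arm?** The subject listing in 8.1.11 and the full deviation list in SAP 5.8. Neither is specified as a by-arm summary. Other treatments for the disease that are not on the prohibited list are also allowed under protocol 5.9.2.1 and need not appear as deviations.

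**Step 4: what can a pooled figure hide?** The arm split is an assumption. If all 28 had been randomised 3:1, the split would be 28 × 3/4 = 21 and 7. If all had been randomised 2:1, it would be 28 × 2/3 = 18.7, so about 19 and 9. Take 20:8 as a value in between, and suppose 7 subjects used rescue or prohibited therapy (an arbitrary number). The pooled table shows 7/28 = 25.0% under every split. The extremes it allows are:

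| Assumed split (active:placebo) | All 7 on active | All 7 on placebo |
|---|---|---|
| 21:7 | 7/21 = 33.3% v 0% | 0% v 7/7 = 100% |
| 20:8 | 7/20 = 35.0% v 0% | 0% v 7/8 = 87.5% |
| 19:9 | 7/19 = 36.8% v 0% | 0% v 7/9 = 77.8% |

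The pooled percentage does not indicate even the direction of a difference. This is a property of pooling, not a prediction for this trial.

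**The case against.** The strongest reply is that nothing is lost. Use is recorded per subject with dates, a listing is planned, prohibited use is logged as a deviation, and 28 subjects can be counted by hand after unblinding. That stands. A reader might infer from 8.1.11 that rescue use cannot be compared between arms, and the documents do not support that. What is missing is a pre-specified by-arm summary.

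A second reply is that silence about treatment need not mean pooling. Sections 8.1.4 and 8.1.6 also omit it, and the sponsor surely does not intend to pool adverse events across arms. SAP 8.1.8 plans one line per cohort and then separate lines for two placebos, so the word cohort is used loosely. SAP 8.1 also has presentations sorted by increasing dose level where appropriate. This weakens the inference about intent. It does not supply the missing level, because 8.1.11 does not cite the reporting standards that 8.1.4 and 8.1.6 rely on, and sorting sets an order, not a grouping.

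A third reply is that harm is assumed. This also stands. The documents give no rescue rate and no expected difference between arms. The study is exploratory, with no hypotheses or decision rules (SAP 4.1, 4.2).

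**Conclusion.** The point holds as a cheap improvement to a descriptive table. As written, the planned summary combines PF-06817024 and placebo, and only the listing and the deviation list would let a reader see whether therapy allowed by protocol 5.9.1 and 5.9.2.1 differed between arms. No estimate, error rate or sample size depends on it.

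The conclusion assumes that 8.1.11 means what it literally says. The 7/28 example rests on an assumed arm split and an arbitrary count.

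Three further inferences are tempting but not supported:
- That rescue is likely to differ between arms. Nothing in the documents establishes this.
- That the disease-activity summaries share the gap. Those sections are redacted and may deal with rescue.
- That the rescue argument covers Part 1. Protocol 5.8.1 has those subjects abstain, apart from treatment of adverse events and limited sponsor-approved non-prescription drugs.

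**What to change.** In SAP 8.1.11, change the grouping to *by study part, cohort and treatment (PF-06817024 v placebo)*, keeping the whole-study summary with the same treatment split.

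For Parts 2 and 3, add one descriptive table by treatment of subjects who used any therapy listed in protocol 5.9.1 (Part 2) or 5.9.2 (Part 3). Give the number, the percentage and the study day of first use. For Part 3, split the table at Week 16, a boundary the protocol already uses: for possible replacement after prohibited treatment (5.9.2) and for keeping concomitant drugs unchanged (5.9.2.1).

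The cost is one line of SAP wording and one extra table. Treatments and dates are already recorded, so there is no new data collection and no change to any clinical rule.

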8.1.12. Screening and Other Special Purpose Data

Prior medication(s) and non-drug treatment(s), serum FSH concentrations, urine drug screen, serum or urine B-hCG for all females of childbearing potential, and urine or blood cotinine concentration will be obtained at Screening.

These data will not be brought in-house, and therefore will not be listed.

Appendix 1. Categorical Classes for ECG and Vital Signs of Potential Clinical Concern

Categories for QTcF

QTcF (ms)	450≤ max. <480	480≤ max.<500	max. ≥500
QTcF (ms)	$30 \le \max. \le 60$	max. ≥60	
increase from			
baseline			

[figure not shown]
Categories for PR and QRS

PR (ms)	max. ≥300	
PR (ms) increase	Baseline >200	Baseline ≤200 and
from baseline	and max.	max. ≥50%
	\geq 25% increase	increase
QRS (ms)	max. ≥140	
QRS (ms)	≥50% increase	
increase from		
baseline		

Categories for Vital Signs

Systolic BP (mm Hg)	min. <90	
Systolic BP (mm Hg)	max. decrease ≥30	max. increase ≥ 30
change from baseline		
Diastolic BP (mm Hg)	min. <50	
Diastolic BP (mm Hg)	max. decrease ≥20	max. increase ≥ 20
change from baseline		
Supine pulse rate (bpm)	min. <40	max. >120
Standing pulse rate (bpm)	min. <40	max. >140

Measurements that fulfill these criteria are to be listed in report.

[figure not shown]
CCI			
-			

CCI		
	-	

CCI

[figure not shown]
CCI		

CCI			
CCI			
CCI			

[figure not shown]

CCI

CCI	

CCI						
			I		I	

CCI		

CCI	

CCI
